### ***3.4 Safety Endpoints***

This is an observational study so safety endpoints are not applicable

## 4 Subject Selection and Withdrawal

### 4.1 Inclusion Criteria

In order to be eligible to participate in the study, a subject must meet the following criteria:

- Born at neonatal department, Bao'an Maternal and Child Health Hospital
- Gestational age < complete 32 weeks
- Parenteral consent is signed by at least one of the two parents

### 4.2 Exclusion Criteria

Subjects who meet any of the following criteria will be excluded from the participation of the study:

- Major congenital abnormalities or birth defects
- Serious perinatal complications such as serious asphyxia or meconium aspiration syndrome.
- Life expectancy < 48 hours

### 4.3 Subject Recruitment and Screening

When infants are admitted to the Neonatal department, parents are informed about this observational study and the possibility to participate by the principal investigator. Signed parenteral consent is required to enter the study. Subjects should be recruited and the first blood sampling will be performed within the first 48 h of life.

### 4.4 Withdrawal of Subjects

A subject will be withdrawn from the study in one of the following conditions:

- The consent is withdrawn by parents prior to the expected completion of the patient
- The principal investigator reserves the right during the study to withdraw a patient from the study if the patient's conditions are evaluated to be not suitable for blood sampling. In this occasion, another patient needs to be recruited to replace the drop-out patient.
- Any infants that die before the completion of 4 postnatal weeks and are not diagnosed with LOS, NEC or chorioamnionitis beforehand will be withdrawn from the study. In this occasion, another patient needs to be recruited to replace the drop-out patient.

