## 1.1 Background

Every year, approximately 15 million infants are born preterm (< 37 weeks of gestation) and 1 million die (1). Preterm infants, especially those are born < 32 weeks of gestation, have immature gastrointestinal tract and innate immune system, which lead to high risks of development of necrotizing enterocolitis (NEC, a devastating intestinal disease affecting 7% preterm infants) and early life systemic infection (late-onset sepsis, LOS, up to 20-40% all hospitalized infants) (1,2). Those infectious diseases may lead to further long-term complications such as neurodevelopmental delay (1). NEC is very often related to LOS, possibly because an abnormal gut bacterial colonization and high gut permeability allow bacterial translocation (3). Conversely, a systemic inflammatory insult may predispose to NEC via impaired gut motility and immunity. As a result, in clinical trials, diagnostic markers are often used for combined LOS and/or NEC. Despite tremendous efforts to develop diagnostic markers for LOS and NEC, none of them are specific enough for clinical use (4). The current “gold standard” of blood culturing for diagnosis of LOS has many highly false negatives and is time-consuming whereas patients may develop septic shock and die shortly after clinical presentation. Ng et al performed a proteomic study to characterize protein biomarkers for LOS and NEC, but their work was exploratory without detailed focus on the mechanism based on an conventional LC-MS protocols (4). Recently, new mechanisms have been suggested to play role in the pathogenesis of adult sepsis such as circulating neutrophil extracellular traps (NETs), microparticles and miRNA but they have not been characterized in neonatal diseases (5,6).

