### **5.3 Sample selection, analysis and comparison**

At the end of the study, the selection of appropriate samples for analysis will be conducted by all investigators of the study. Samples included in the analysis are those collected from birth until the disease diagnosis or completion of 4 postnatal weeks. In case of clinical diagnosis of LOS and/or NEC before completion of 4 weeks, further routine sample collection after diagnosis is continued if feasible.

Temporal samples will be analyzed to perform three separate comparisons:

- Infants without versus with LOS and/or NEC
- Infants without versus with clinical/histological chorioamnionitis
- Infants with major or minor amount of mother's own milk during the first two weeks of life ( $\geq$  or < 50% of feeding times as complete mother's own milk).

Plasma proteomic study will be prioritized and will include as many samples as possible, followed by validation with absolute quantification of potential proteins using immune assays. The type of other -omic analysis for plasma (miRNA profiling) whole blood (transcriptomics or epigenetics) as well as sample size will be decided depending on the results of proteomic study.

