## **9 Ethical Considerations**

This study is to be conducted according to applicable government guidelines and regulations and Institutional research policies and procedures.

This protocol and any amendments will be submitted to the Ethical Committee at Bao'an Maternal and Child Hospital, Shenzhen for formal approval of the study conduct. The decision of the Ethical Committee concerning the conduct of the study will be made in writing to the investigators.

All subjects for this study will be provided a consent form in Chinese describing this study and providing sufficient information for subjects to make an informed decision about their participation in this study. The consent form will be submitted with the protocol for review and approval by the Ethical Committee for the study. The formal consent of a subject must be obtained before that subject is submitted to any study procedure. This consent form must be signed by the subject or legally acceptable surrogate, and the investigator-designated research professional obtaining the consent.

Blood samples obtained for this cohort are left-over sample materials from routine clinical blood sampling for screening and diagnosis in preterm infants at the local hospital (Neonatal Department, Bao'an Maternal and Child Health Hospital, Shenzhen). Therefore, there are no potential harmful effects of blood sampling to the participating infants.

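### Section 4.4 allows an infant judged unsuitable for blood sampling to be withdrawn and replaced, without exempting diagnosed infants or saying that earlier data are kept, so the cohort can be selected on severity of illness

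*Protocol*

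**What the plan says.** Protocol section 4.4 opens its list with "A subject will be withdrawn from the study in one of the following conditions". Three conditions follow.

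- **First bullet:** the parents withdraw consent.
- **Second bullet:** the principal investigator holds a right, not a duty, to withdraw an infant whose "conditions are evaluated to be not suitable for blood sampling. In this occasion, another patient needs to be recruited to replace the drop-out patient".
- **Third bullet:** infants who die before the end of the fourth week and "are not diagnosed with LOS, NEC or chorioamnionitis beforehand will be withdrawn from the study". They too are replaced.

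Section 5.3 limits the analysed samples to those taken between birth and diagnosis, or up to four weeks. For an infant diagnosed with LOS and/or NEC earlier than that, "further routine sample collection after diagnosis is continued if feasible". Section 9 describes the study blood as "left-over sample materials from routine clinical blood sampling for screening and diagnosis in preterm infants". Section 5 has the blood volume judged at each sampling period, with health status as one consideration. Section 8.2 already provides the CRF entry N/D for a procedure that was not done.

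Section 3.2 makes markers for the prognosis and/or diagnosis of LOS and/or NEC a primary endpoint. Section 6.1 expects clinical LOS and/or NEC in 20-30% of 200 infants.

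**The concern.** Under the second bullet, an infant who cannot be sampled may lose its place in the cohort, not just one sample. The trigger is the infant's condition, which is plausibly related to the outcome under study. The bullet has no exemption by diagnosis, although the bullet after it does.

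A diagnosed infant who dies therefore stays in the study, while a diagnosed infant who survives but is judged unsuitable for sampling can be withdrawn and replaced. An infant who deteriorates before any diagnosis can also be withdrawn, and its case status may then never be recorded.

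If the rule is used in this way, the LOS/NEC group loses some of its more severe members, and replacement brings the cohort back to 200 without bringing those cases back. The marker comparison and the ROC analysis would then lean towards milder disease, and the observed LOS/NEC rate would be too low. Withdrawal and replacement take place during recruitment, so an analysis plan cannot recover follow-up that was never collected.

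**Working it through.** **1. The passages side by side**

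| Situation | Where | What happens to the infant |
|---|---|---|
| Dies, diagnosed beforehand | 4.4, third bullet | Not withdrawn under this bullet |
| Dies, no diagnosis | 4.4, third bullet | Withdrawn and replaced |
| Judged unsuitable for sampling, any diagnosis or none | 4.4, second bullet | May be withdrawn; if so, replaced |
| Diagnosed, further sampling not feasible | 5.3 | Sampling stops; withdrawal is not mentioned |

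A diagnosed infant who can no longer be sampled falls under both of the last two rows, and the protocol does not say which governs. The lead-in is worded as mandatory and the second bullet as a right, so it is also unclear how often the bullet is meant to be used.

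**2. What happens to data already collected**

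Section 8.1 settles this only for revoked authorization, where information collected earlier may still be used. For withdrawal under the second bullet the protocol is silent.

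**3. The protocol's own figures**

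The 200 infants come from admission rate and sampling capacity. Section 6.1 gives no error rates, effect size or withdrawal rate, so there is no calculation to reproduce. Expected cases are 200 × 0.20 = 40 to 200 × 0.30 = 60. The expected share of non-cases among replacements is 1 − 0.30 = 70% to 1 − 0.20 = 80%.

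**4. Illustration: number of cases**

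Assumptions, none of them from the protocol:
- A share w of cases and no non-cases is withdrawn.
- Withdrawn infants do not count in the final cohort.
- Replacements have the same risk p and fall under the same rule.

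The case share in the final 200 is then p(1 − w)/(1 − pw), and the number enrolled is 200/(1 − pw).

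| p | w | Case share | Cases in final 200 | Enrolled |
|---|---|---|---|---|
| 20% | 0 | 20% | 40 | 200 |
| 20% | 10% | 0.18/0.98 = 18.4% | 36.7 | 204.1 |
| 20% | 20% | 0.16/0.96 = 16.7% | 33.3 | 208.3 |
| 30% | 0 | 30% | 60 | 200 |
| 30% | 10% | 0.27/0.97 = 27.8% | 55.7 | 206.2 |
| 30% | 20% | 0.24/0.94 = 25.5% | 51.1 | 212.8 |

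The net loss is 3.3 to 8.9 cases (40 − 36.7 to 60 − 51.1). It is smaller than the number withdrawn, because some replacements become cases themselves.

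**5. Illustration: direction of the marker effect**

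Assume a marker that is 1 SD higher in cases and correlated ρ = 0.3 to 0.7 with severity, and that the most severe share w of cases is lost. With c = Φ⁻¹(1 − w), the mean difference becomes 1 − ρφ(c)/(1 − w).
- w = 10%, ρ = 0.3: difference 0.942 SD, AUC 0.749.
- w = 20%, ρ = 0.7: difference 0.755 SD, AUC 0.713.

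Without any loss the AUC is Φ(1/√2) = 0.760. These values show direction only.

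**The case against.** A reader might infer that the sickest LOS/NEC infants do leave the cohort and take their birth and first-week samples with them. The documents do not support this.

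- **Withdrawal is discretionary.** The second bullet gives the investigator a right. Loss of severe cases is something the text permits, not something it states will happen.
- **No section says earlier samples or diagnoses are discarded.** Section 5.3 analyses samples only up to diagnosis. If data up to withdrawal are kept, an infant withdrawn after diagnosis loses nothing from that set.
- **Unsuitability need not mean LOS or NEC.** Section 5 names body weight beside health status, and section 5.2 records RDS, BPD and pneumonia. Section 5.1 defines clinical LOS by blood values, so an infant with that diagnosis has already had clinical blood drawn. The remark in section 1.1 that "patients may develop septic shock and die shortly after clinical presentation" is about the slowness of blood culture, not about fitness for sampling.
- **Section 5.3 suggests that diagnosed infants stay with missed samples.** A discretionary right can coexist with that.

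These points limit the claim but do not remove it. Discretion tied to the infant's condition, used by someone who may know the diagnosis, is itself a route to selection. Silence on retention leaves the damaging reading open. If section 5.3 shows the intention, the second bullet should say the same. Section 9 strengthens this: if the study uses only left-over blood, it is hard to see when study sampling alone would call for withdrawal.

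**Conclusion.** The point holds as a defect in the rule, not as a demonstrated bias. The second bullet of section 4.4 allows withdrawal with replacement that depends on the infant's condition, has no exemption for diagnosed infants, and does not say whether earlier data are kept. It conflicts with the third bullet and fits poorly with sections 5.3 and 9. The comparison at risk belongs to a primary endpoint.

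The size cannot be derived from the protocol. The illustrated fall in cases, about 3 to 9 of an expected 40 to 60, rests on three assumptions: 10-20% of cases withdrawn, no non-cases withdrawn, and withdrawn infants not counted. If unsuitability is unrelated to LOS/NEC and its severity, or if withdrawn infants' samples and diagnoses are kept and analysed, the effect is smaller and may be negligible. The case for change rests on the conflict between the passages and on how little the change costs.

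**What to change.** Reconcile the second bullet of section 4.4 with the third bullet and with section 5.3:

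- An infant judged unsuitable for blood sampling misses that sample, or later samples as well, recorded as N/D with the reason as section 8.2 provides. Whether an infant is suitable remains the investigator's clinical judgement.
- The infant stays in the cohort with all earlier samples, diagnoses and continued CRF follow-up, and is not replaced.
- Missed samples are reported by reason and by diagnosis group.

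The consent and death bullets stay as they are. The change concerns cohort membership only, not when an infant is bled. The cost is one short amendment and a few incomplete sample series that are not made up by new recruits.

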During pregnancy and labor, 20% of term and up to 60% of preterm deliveries show signs of maternal/prenatal inflammation (7), chorioamnionitis, which is the most important risk factor for preterm birth. Prenatal inflammation is associated with postnatal gut and systemic inflammation in newborn infants (8) and this may affect immune development in several ways. However, no study has yet investigated whether parameters related to postnatal immune development in preterm infants are affected by chorioamnionitis, and how immune parameters in infants with chorioamnionitis are associated with postnatal infections. Further, it is unclear how important the progression of enteral feeding with milk (mother's own milk, donor milk or formula) is for the postnatal NEC and LOS sensitivity. We speculate that early feeding with an optimal milk diet may help to support both gut and systemic immunity development, and thereby increase the resistance against NEC and LOS.

To improve the understanding of NEC and LOS, and their diagnostic criteria, and the postnatal immune development after chorioamnionitis, we investigate temporal blood samples in n=200 preterm infants. We apply proteomics and several immune assays to plasma, as well as whole blood transcriptomics/epigenetics to blood collected from preterm infants with and without NEC, LOS and/or CA. The aim is to identify new proteins and transcriptomic/epigenetic parameters that are related to the mechanisms of NEC, LOS and CA. These biological markers may help to provide possible new diagnostic markers for neonatal LOS and NEC, with and

without maternal chorioamnionitis and with/without difficulties in establishing normal enteral feeding.

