### 5.1 Diagnosis of chorioamnionitis, LOS and NEC

Once the patient is recruited, information about diagnosis of chorioamnionitis is collected and filled in the CRF. Clinical chorioamnionitis is defined in pregnant women with fever ( $\geq 38^{\circ}\text{C}$ ), high heart rate ( $\geq 100/\text{min}$  for mothers and  $\geq 160/\text{min}$  for fetuses), as well as when plasma CRP and blood leukocyte counts  $\geq 20 \text{ mg/L}$  and  $12,000 \text{ leukocytes/mm}^3$ . Histological chorioamnionitis is confirmed after histologic examination of the fetal membranes.

LOS is defined as sepsis occurring after 72 hours after birth. Clinical diagnosis of LOS is defined when the patient shows two or more of the following criteria: white blood cell count  $< 5 \times 10^9 \text{ cells/L}$  or  $> 20 \times 10^9 \text{ cells/L}$ , total platelet count  $< 100 \times 10^9 \text{ cells/L}$ , CRP  $> 10 \text{ mg/L}$ , procalcitonin  $> 2 \text{ ng/mL}$ . Culture-proven sepsis is defined as clinical sepsis with positive blood bacterial culture result.

Diagnosis of NEC is based on the conventional Bell system (IA, IB, IIA, IIB, IIIA and IIIB). Medical NEC is defined when an infant is diagnosed at stage IA to IIB. When an infants is classified with Bell stage III A or B (advanced NEC and bowel perforation), surgical interventions is required (surgical NEC).

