## 6 Statistical Plan

### 6.1 Sample Size Determination

Based on the practical issues of admission rate of preterm infants and capacity of temporal blood sampling at the Neonatal Department, we anticipate to include 200 preterm infants (< 32 weeks of gestation) with estimated rate of clinical chorioamnionitis of 15-20% (for overall preterm cases, 40-70% of premature PROM cases), and clinical LOS and/or NEC of 20-30%.

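### Deaths before 4 weeks are withdrawn and replaced only when none of the three study diagnoses was made, so the undiagnosed controls are selected on survival

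*Protocol*

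**What the plan says.** Section 4.4 of the protocol lists three grounds for withdrawal. The third reads: "Any infants that die before the completion of 4 postnatal weeks and are not diagnosed with LOS, NEC or chorioamnionitis beforehand will be withdrawn". The next sentence adds: "In this occasion, another patient needs to be recruited to replace the drop-out patient". Nothing is said about infants who die after one of the three diagnoses, so they remain in the study.

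Section 5.3 sets the comparisons. One is LOS and/or NEC, yes or no. Another is "Infants without versus with clinical/histological chorioamnionitis". Both correspond to primary endpoints in section 3.2. The third comparison, by amount of mother's own milk, is secondary. The sample window in section 5.3 closes at diagnosis or at 4 weeks; death is not mentioned.

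On timing, section 4.3 places the first blood sample in the first 48 hours of life. Section 5.1 states: "LOS is defined as sepsis occurring after 72 hours after birth". On histology it states: "Histological chorioamnionitis is confirmed after histologic examination of the fetal membranes".

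**The concern.** Whether an enrolled infant counts depends on two things together: a later event (death), and the diagnoses that define the groups. An infant with no diagnosis is kept only by living 4 weeks. A diagnosed infant is kept either way. If marker levels differ between infants who die and infants who live, this can distort the marker associations in both primary comparisons and the ROC performance of the panel planned in section 6.2. The milk comparison loses the same infants, from both feeding groups.

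This is a stated rule, not a detail left to an analysis plan. If the removed infants are gone from the cohort and others have taken their places, a later analysis cannot easily restore them.

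**Working it through.** **1. Does any other section bring these infants back?**
- Section 4.2 excludes at entry only a life expectancy under 48 hours, major anomalies and serious perinatal complications. The death rule acts later, on enrolled infants who may already have been sampled.
- Section 8.1 keeps earlier data when authorization is revoked. It does not cover death.
- Section 5.3 does not mention death.

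None of these sections restores them.

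**2. Who is selected on survival?**

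| Infant who dies before 4 weeks | Outcome under section 4.4 |
|---|---|
| Chorioamnionitis, no LOS/NEC | stays, as a LOS/NEC control |
| LOS/NEC, no chorioamnionitis | stays, as a chorioamnionitis control |
| Both | stays |
| None of the three | withdrawn and replaced |

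Each control group is thus partly selected. Among LOS/NEC controls the treatment of death depends on chorioamnionitis status.

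**3. How large is the undiagnosed group?** The protocol gives no figure for it, so there is none to reproduce. Inputs from section 6.1 are N = 200, an "estimated rate of clinical chorioamnionitis of 15-20" per cent (c), and a clinical LOS/NEC rate of 20-30% (p). Independence of the two is my assumption.

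Undiagnosed = 200 × (1 − c) × (1 − p):
- c = 0.15, p = 0.20: 136
- c = 0.15, p = 0.30: 119
- c = 0.20, p = 0.20: 128
- c = 0.20, p = 0.30: 112

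LOS/NEC controls = 200 × (1 − p) = 140-160; the undiagnosed share is 1 − c = 80-85%.
Chorioamnionitis controls = 200 × (1 − c) = 160-170; the undiagnosed share is 1 − p = 70-80%.

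**4. How far do the assumptions matter?**
- *Overlap.* With no overlap between the conditions, the lowest shares are (1 − 0.20 − 0.30)/0.70 = 71% of LOS/NEC controls and 0.50/0.80 = 62.5% of chorioamnionitis controls. Section 1.1 points the other way: "Prenatal inflammation is associated with postnatal gut and systemic inflammation in newborn infants". Positive association raises both shares above the independence values.
- *Histological cases.* Section 6.1 plans only on clinical disease, while section 5.3 also counts histological disease. Section 1.1 says that "up to 60% of preterm deliveries show signs of maternal/prenatal inflammation". At c = 0.60, 200 × 0.40 × (0.70 to 0.80) = 56-64 infants are undiagnosed. That is 40% of LOS/NEC controls and still 70-80% of the 80 chorioamnionitis controls.

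**5. How many infants would be removed?** The mortality q among undiagnosed infants is an assumption. Removed = q × 112 to q × 136: 2.2-2.7 at 2%, 5.6-6.8 at 5%, 11.2-13.6 at 10%. At c = 0.60 and q = 10% it is 5.6-6.4.

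**6. What could that do to an AUC?** This is an illustration on assumptions only. Let cases lie 1.0 SD above surviving controls, so AUC = Φ(1/√2) = 0.760. Let the dying infants lie s SD towards the cases. Keeping them gives AUC = (1 − q) × 0.760 + q × Φ((1 − s)/√2). For s from 0.5 to 1.5:
- q = 2%: 0.758 to 0.752, a change of 0.002-0.008
- q = 5%: 0.754 to 0.740, a change of 0.006-0.020
- q = 10%: 0.748 to 0.720, a change of 0.012-0.040

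This treats every control as selected. If a share e of controls escapes the rule, the change is multiplied by (1 − e)(1 − q)/(1 − (1 − e)q). For e = 0.15-0.20 and q = 10%, the largest change falls from 0.040 to 0.031-0.033.

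**The case against.** The strongest defence concerns LOS/NEC. An infant who dies on day 5 has not been shown to be free of disease, and calling that infant a control could misclassify. This stands as a reason for care, but it does not justify the rule. It has no bearing on chorioamnionitis, and the rule does not follow it consistently: an exposed infant who dies without LOS/NEC stays a control, and an unexposed one is removed.

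The likely effect may also be modest. The entry exclusions in section 4.2 should lower later undiagnosed deaths. With 50 cases and 150 controls (25% of 200), the Hanley-McNeil standard error at an AUC of 0.76 is about 0.04, so even the worst case illustrated is no more than about one standard error. Sampling error does not excuse bias, but this bears on how much weight the point carries in a marker study sized on feasibility.

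Three stronger readings are tempting and are not supported:
- *False-negative cultures leave LOS cases among the removed infants.* Section 1.1 does criticise cultures, but section 5.1 allows a clinical LOS diagnosis on two of four blood criteria without a positive culture. What remains is rapid death before diagnosis, which section 1.1 makes plausible.
- *Histological cases will be dropped.* That follows only if the prior-diagnosis condition in section 4.4 is read strictly. The protocol gives no histology turnaround and does not say that a result arriving after death is ignored.
- *Marker performance will be inflated.* The illustration assumes that dying infants resemble cases. Nothing in the protocol establishes that.

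**Conclusion.** The point holds: section 4.4 makes retention of undiagnosed infants, and only of them, conditional on 4-week survival. It is firmest for the chorioamnionitis comparison. For LOS/NEC the fault is the inconsistent handling of deaths, and the possible loss of infants who died before LOS or NEC was diagnosed.

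The affected group is about 112-136 of 200 at the planned clinical rates under independence, and 56-64 if 60% of infants had chorioamnionitis. The bias itself cannot be sized. The only mortality figure, in section 1.1, is about 1 million deaths among 15 million preterm births (1/15 = 6.7%). It is global, covers all causes and births before 37 weeks, and is not this cohort's rate among undiagnosed infants. If that mortality is low the bias is small; if markers do not differ by survival it does not arise. The rule should be changed because the correction is cheap, not because a large distortion has been shown.

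**What to change.** In section 4.4, delete the withdrawal for death and leave the consent and sampling-suitability withdrawals as they are. Keep these infants' samples up to death, and add death as an end of the sample window in section 5.3. Classify chorioamnionitis by its final recorded status, whenever the histology result arrives. Additional infants may be recruited, but must not replace the deceased in the analysis.

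Report deaths by group. For LOS/NEC, compare cases with infants alive and under observation at the same age, and add a sensitivity analysis for undiagnosed deaths. Comparing at the same age also deals with infants who die within 72 hours and so could never meet the LOS definition. These analysis details can sit in a statistical analysis plan.

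The cost is a wording amendment for the Ethical Committee (section 9). No extra blood is needed, since section 9 describes the samples as left over from routine care. Some infants will have incomplete sample series. The target of 200 is a feasibility figure in section 6.1, so no power calculation is affected.
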